#### 7.1.2. Serious adverse event (SAE)

A Serious Adverse Event is any untoward medical occurrence that at any dose:

- Results in death
- Is life threatening
- Requires inpatient hospitalization or prolongation of existing hospitalization
- Results in persistent or significant disability/incapacity, or
- Is a congenital anomaly/birth defect
- Is an important medical event.

The term "life threatening" refers to an event in which the subject was at risk of death at the time of event; it does not refer to an event that hypothetically might have caused death if it was more severe.

Inpatient hospitalization is considered to have occurred if the subject is admitted to the hospital on an in-patient basis, even if released the same day. Prolongation of hospitalization is defined as an additional night stay in the hospital. Hospitalization for a diagnostic test (even if related to an AE) or elective hospitalization that was planned before study enrollment (signing the ICF) is not themselves reasons for an event to be defined as a SAE.

Important medical events are those that may not be immediately life threatening, result in death or hospitalization, but are clearly of major clinical significance and may jeopardize the subject or require intervention to prevent one of the outcomes listed in the SAE definition above. These should also usually be considered serious. Examples of such events are intensive treatment in an emergency room or at home for allergic bronchospasm, blood dyscrasia or convulsions that do not result in hospitalization.

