#### 7.1. Definitions

#### 7.1.1. Adverse events (AE)

An AE is any untoward medical occurrence in a patient or clinical investigation subject administered a study medication(s) and which does not necessarily have a causal relationship with the study medication. An AE can therefore be any unfavorable and unintended sign or symptom associated with the use of a study medication (including an abnormal laboratory finding), whether or not related to the study medication.

Thus any new, clinically relevant worsening of an existing sign, symptom or disease, should be considered an AE.

Worsening of any of the target lesion assessments should be reported as an AE ONLY if the use of the study medication is interrupted or discontinued or if therapy is required to manage the event.

The investigator must, for any AE associated with a target lesion, question the subject in detail to determine if there are any confounding factors (*e.g.*, irritation by clothing or activity, sunburn) for any such AE.

Report any event that requires use of the eyewash kit [Section 5.7.6] as an AE for "eye irritation". For all AEs of this type:

- Contact the medical monitor (see contact information on Page 1, or in Section 7.2.2) immediately (within 24 hours)
- Unblind the study medication for the subject (Section 5.10.2)
- Arrange for the subject to be transported to the most appropriate hospital emergency room (ER) and provide the study medication identification information to the appropriate ER staff
- Follow the course of the AE
- Report the event as an SAE if appropriate (Section 7.1.2).

Every new episode or clinically relevant worsening of a chronic condition (*e.g.*, headaches, seasonal allergies, depression, and hypertension) should be reported as a separate AE, even if the condition is reported in the subject's medical history.

The investigator should, when certain, report a diagnosis rather than the signs, symptoms or clinically relevant abnormal laboratory values associated with the AE. Otherwise, signs, symptoms or abnormal laboratory values may be used to describe the AE.

Any CR abnormality discovered prior to the first study medication application should be reported as medical history, not as an AE.

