## 7.2.2. Procedure for reporting a serious adverse event

Upon becoming aware of a SAE occurring during the AE reporting period, whether or not related to the study medications, the investigator must:

- 1. Take the appropriate medical action to ensure the subject's safety
- 2. Immediately inform the Medical Monitor of the SAE by telephone:

[name]. Aclaris Therapeutics, Inc. [name] Office [contact] Mobile [contact] SAE [contact] E-mail: [contact]

- 3. Within 24-hours complete, as fully as possible, an AE CRF and an SAE form; fax or e-mail the forms and any other relevant information (*e.g.*, concomitant medication CRF, medical history CRF, laboratory test results) to the Aclaris Therapeutics, Inc. Medical Monitor.
- 4. Monitor and document the progress of the SAE until it resolves or, if not resolved after the subject's last study visit, until in the opinion of the investigator the AE reaches a clinically stable outcome with or without sequelae AND the investigator and Aclaris Therapeutics, Inc. Medical Monitor agree that the SAE is satisfactorily resolved.
- 5. Inform the Aclaris Therapeutics, Inc. Medical Monitor of SAE updates by telephone followed by an SAE form update sent by fax or by e-mail.

Page 47 of 56 Date: 01-JUL-2014 6. Comply with the appropriate regulatory requirements and Aclaris Therapeutics, Inc. instructions regarding reporting of the SAE to the responsible Institutional Review Board (IRB) or Ethics Committee (EC).

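### Section 7.1.2 counts any inpatient admission as serious, then exempts admission for a diagnostic test even when an AE prompted it

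*Combined protocol and SAP*

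**What the plan says.** Section 7.1.2 lists the seriousness criteria. One of them is "Requires inpatient hospitalization or prolongation of existing hospitalization". The explanatory text says this has occurred once the subject is "admitted to the hospital on an in-patient basis, even if released the same day". The reason for the admission plays no part in that test.

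The same paragraph then carves out two kinds of admission. The sentence opens "Hospitalization for a diagnostic test (even if related to an AE) or elective hospitalization that was planned before study enrollment (signing the ICF) is not", and its full predicate is "is not themselves reasons for an event to be defined as a SAE". The parenthesis expressly extends the diagnostic-test part to admissions connected with an AE.

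SAE status decides how an event is handled. The steps in Section 7.2.2 start "Upon becoming aware of a SAE occurring during the AE reporting period, whether or not related to the study medications". They are an immediate telephone report to the Medical Monitor, an AE CRF and an SAE form within 24 hours, follow-up that ends only when the investigator and the Medical Monitor agree, and SAE reporting to the IRB or EC as the rules require. Section 7.1.4 opens the SAE reporting window at signature of the ICF, but opens the window for non-serious AEs only at the first study medication application.

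**The concern.** Inpatient admission is one of the few seriousness criteria that needs no clinical judgement: the subject was admitted or was not. The exemption takes that objective trigger away when an AE has led to admission for work-up. At that moment the diagnosis is often still open, so the remaining, more judgemental criteria are hardest to apply. Two sites with the same event could classify it differently, one relying on the criterion and the other on the exemption.

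What is at stake is safety classification and speed of reporting. Efficacy is not touched.

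**Working it through.** No arithmetic applies, and the plan states no figure on this point. The check sets the sections side by side.

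**Step 1: the same event under both rules.** Take an unplanned inpatient admission, solely for tests, to investigate an on-study AE that meets no other criterion. Under the criterion in Section 7.1.2 it is serious, because the subject was admitted. Under the exemption in the same section, the admission does not make it serious. Nothing else in the protocol narrows the exemption, for instance to tests that were scheduled in advance.

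**Step 2: does the restriction to planned admissions cover diagnostic tests too?** The words on planning before enrollment follow the elective limb. If they also governed the diagnostic limb, the parenthesis would have little left to do, since an admission arranged before consent would seldom be related to an on-study AE. The natural reading is that unplanned admissions for AE work-up are exempt.

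**Step 3: what changes with the classification.**

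| | Classed as an SAE (7.2.2) | Non-serious AE after first application | Non-serious event between ICF and first application |
|---|---|---|---|
| Record | AE CRF and SAE form within 24 hours | AE CRF (7, 7.2.1) | None required by 7.1.4 |
| Notice to Medical Monitor | Immediate, by telephone | None specified, except for eyewash events (7.1.1) | None specified |
| Follow-up | To resolution or a stable outcome, with the Medical Monitor's agreement | Related: to resolution or a stable outcome in the investigator's opinion. Not related: to resolution or the last visit (7.2.1) | None specified |
| IRB/EC SAE reporting | As required | Not triggered | Not triggered |

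**Step 4: the screening period.** Section 7.1.1 sends clinically relevant abnormalities found before the first application to medical history. Section 5.3.2 does ask about health changes at Visit 2 before randomization and calls for AEs to be reported, but it refers to Section 7.2.1, which is tied to the reporting period in Section 7.1.4. An exempted event in this period may therefore produce no AE record.

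**The case against.** **The sentence removes one criterion and does not declare events non-serious.** This stands in full. A reader who stops before the end of the sentence might infer that the event is made non-serious outright. The predicate does not support that: death, threat to life, disability, congenital anomaly and important medical event all still apply. The important-medical-event route is a partial backstop only. It needs clear major clinical significance, and the text says of such events "These should also usually be considered serious", which leaves room for judgement.

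**A specific exception after a general rule is not a contradiction.** This stands in part. The text can be followed as it is, and the sponsor may have intended it. The result is still that an AE-driven admission can fall outside SAE reporting.

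**The planning condition may govern both limbs.** Section 7.1.1 treats worsening of a chronic condition as a new AE, so an admission planned before consent could be related to an AE and the parenthesis would keep some meaning. The reading is possible but strained, and if it was intended, the rewording below says so plainly.

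**Eyewash events.** A reader might infer that these would go without prompt notice. The documents do not support this. Section 7.1.1 requires contact with the Medical Monitor within 24 hours, unblinding, and the step "Arrange for the subject to be transported to the most appropriate hospital emergency room (ER"). Section 5.10.2 then requires discharge from the study. Transport to an emergency room is also not an inpatient admission. These events are not evidence of lost prompt notice.

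**Follow-up.** A reader might infer that all follow-up is lost. It is not: Section 7.2.1 keeps related AEs under follow-up until they resolve or stabilize.

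**Conclusion.** The point holds as a minor defect in safety classification. An unplanned inpatient admission to investigate an on-study AE, meeting no other criterion, is not an SAE under Section 7.1.2 as written. After the first application the loss is limited to the items in the table, and the AE itself is still recorded. Before the first application the gap is wider, because there may be no AE record at all.

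This assumes that the investigator follows the exemption literally, that the admission is inpatient and solely for tests, and that the diagnostic limb is not confined to planned admissions.

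The size cannot be estimated, because the documents give no rate of such admissions. A reader might want to size it by what one event would do to an arm's SAE proportion. That reflects only the weight of one subject in an arm and says nothing about how often the clause would operate. Section 9.2 plans descriptive AE tables without inferential testing and names no table of SAE proportions. The efficacy analyses and the power statement are unaffected.

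**What to change.** Reconcile the two sentences in Section 7.1.2. Delete the parenthesis on relation to an AE, and limit the exemption to diagnostic or elective admissions that were planned before the ICF was signed or were not prompted by an AE. An admission prompted by an AE then stays under the hospitalization criterion. Because SAE reporting starts at consent, the wording should make clear that it also covers untoward events before the first application.

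If the sponsor prefers to keep the exemption, the section should at least state how an unplanned inpatient admission to investigate an AE is classified.

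The cost is one sentence and possibly a few more SAE forms. Sample size, visits and analyses do not change.

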## 7.1.3. Unexpected adverse event

An AE is considered unexpected if it is not listed in the Investigator Brochure or is not listed at the specificity or severity that has been observed.

## 7.1.4. Adverse event reporting period

The investigator must start reporting non-serious AEs starting with the subject's first study medication application and continuing until the end of the subject's last study visit. Reporting for SAEs must start when the subject signs the ICF and continue until the end of the subject's last visit.

#### 7.1.5. Severity

The investigator is to define the severity of each AE using the following definitions as a guideline. The investigator will consider the range of the possible severity of the event and identify the severity that is the most appropriate according her/his medical judgment.

Mild – Awareness of signs or symptom, but easily tolerated

**Moderate** – Discomfort, enough to cause interference with usual activity

**Severe** – Incapacitating with inability to perform usual activity.

# 7.1.6. Relationship to study medication

The investigator will determine if there is a reasonable causal relationship between the study medication and an AE or not. The investigator will use her/his best medical judgment and consider all relevant factors (*e.g.*, temporal relationship, location of the event, the subject's relevant medical history, concomitant therapies and concurrent conditions) to determine the relationship of the AE to the study medication. The investigator will define the relationship of an AE to the study medication by selecting one of the following categories:

**Related** – There is a reasonable possibility that there is a causal relationship between the study medication and the AE.

**Not Related** – There is not a reasonable possibility that there is a causal relationship between the study medication and the AE.

The term "reasonable causal relationship" means there are facts or arguments to suggest a causal relationship (International Conference on Harmonization (ICH) E2A).

## 7.2. **Reporting Procedures**

## 7.2.1. Procedures for reporting adverse events

At each post enrollment visit, the investigator will question the subject to elicit AEs using a non-directive question such as "Has there been any change in your health since the previous study visit?"

The investigator/designee will monitor the subject for at least 20 minutes after the Application Completion Time at Visit 2 and at Visit 4 to elicit AEs in a similar manner.

If appropriate, based on the subject's response to non-directed questioning regarding AEs, the investigator will follow-up with directed questions and appropriate evaluations.

Any AE noted during the reporting period (Section 7.1.4) must be reported in the source documents and on the appropriate AE CRF.

AEs that are defined as "Not Related" to the study medications will be followed until they are resolved or until the subject's last study visit. AEs that are defined as "Related" to the study medications will be followed until they are resolved or, if not resolved after the subject's last study visit, until in the opinion of the investigator, the AE reaches a clinically stable outcome with or without sequelae.

## 7.2.2. Procedure for reporting a serious adverse event

Upon becoming aware of a SAE occurring during the AE reporting period, whether or not related to the study medications, the investigator must:

- 1. Take the appropriate medical action to ensure the subject's safety
- 2. Immediately inform the Medical Monitor of the SAE by telephone:

[name]. Aclaris Therapeutics, Inc. [name] Office [contact] Mobile [contact] SAE [contact] E-mail: [contact]

- 3. Within 24-hours complete, as fully as possible, an AE CRF and an SAE form; fax or e-mail the forms and any other relevant information (*e.g.*, concomitant medication CRF, medical history CRF, laboratory test results) to the Aclaris Therapeutics, Inc. Medical Monitor.
- 4. Monitor and document the progress of the SAE until it resolves or, if not resolved after the subject's last study visit, until in the opinion of the investigator the AE reaches a clinically stable outcome with or without sequelae AND the investigator and Aclaris Therapeutics, Inc. Medical Monitor agree that the SAE is satisfactorily resolved.
- 5. Inform the Aclaris Therapeutics, Inc. Medical Monitor of SAE updates by telephone followed by an SAE form update sent by fax or by e-mail.

Page 47 of 56 Date: 01-JUL-2014 6. Comply with the appropriate regulatory requirements and Aclaris Therapeutics, Inc. instructions regarding reporting of the SAE to the responsible Institutional Review Board (IRB) or Ethics Committee (EC).

## 8. **PREGNANCY**

WOCBP include any female who has experienced menarche and who has not undergone successful surgical sterilization (*e.g.*, hysterectomy, hysteroscopy, bilateral tubal ligation, bilateral oophorectomy or bilateral minilaparotomy) or is not postmenopausal. Postmenopausal is defined as  $\geq$ 12 months with no menses without an alternative medical cause. Women who are WOCBP and are using an active method of birth control, are practicing abstinence or where the partner is sterile (*e.g.*, vasectomy), should be considered to be WOCBP.

All WOCBP must use an effective method of birth control during the course of the study, in a manner such that risk of failure is minimized. Effective methods of birth control approved for use in this study are:

- Implants
- Injectable
- Patch
- Combined oral contraceptives
- Barrier methods (*e.g.*, condom, diaphragm) with spermicide
- ParaGard® and Mirena® intrauterine devices.

Prior to trial enrollment, WOCBP must be advised of the importance of avoiding pregnancy during trial participation and the potential risk factors for a pregnancy. The subject must sign an informed consent form documenting this discussion. During the trial all WOCBP will be instructed to contact the investigator immediately if they suspect they might be pregnant (*e.g.*, missed or late menstrual period).

If a subject or investigator suspects that the subject may be pregnant prior to study medication administration, the study medication must be withheld until the results of a pregnancy test are available. If pregnancy is confirmed, the subject must not receive study medication and must be discharged from the study.

If, following study medication administration, it is determined that the subject may have been or was pregnant at the time of study medication exposure (including at least 2 days after study medication administration) the investigator must immediately notify the Aclaris Therapeutics, Inc. Medical Monitor and record the event on a pregnancy surveillance form. While not an AE or SAE, the investigator must report every pregnancy using a pregnancy surveillance form and follow the reporting procedures described for SAE reporting (Section 7.2.2).

Protocol-required procedures for trial discontinuation and follow-up must be performed on the subject unless contraindicated by pregnancy (*e.g.*, x-ray studies). Other appropriate pregnancy follow-up procedures should be considered if indicated. In addition, the investigator must report to Aclaris Therapeutics, Inc.'s Medical Monitor on the pregnancy surveillance form, follow-up information regarding the course of the pregnancy, including perinatal and neonatal outcome. Infants should be followed for a minimum of six weeks.

# 9. STATISTICAL ANALYSES

## 9.1. Statistical Analysis of Clinical Indices

The primary effectiveness analysis will consist of mean change from baseline to Visit 8 PLA performed using Analysis of Covariance (ANCOVA) with baseline PLA as the covariate. The analysis will be performed at each post-baseline visit with emphasis on Visit 8. Comparisons between vehicle and each active treatment group will be performed within the model using least-squares means and the common error term. The primary efficacy analyses will be based on the per protocol (PP) population, defined as all randomized subjects who completed the study with no major protocol violation.

A secondary efficacy analysis of a separate comparison between each active treatment group and the vehicle treatment group based on the proportion of subjects whose target lesion is judged to be clear on the PLA (PLA = 0) at Visit 8. A separate Cochran-Mantel-Haenszel (CMH) test stratified by Site will be used for each comparison. A secondary efficacy analysis will also be conducted using this same methodology, but based on SSA.

Secondary analyses will initially be performed on the PP population, but will also be performed on the intent-to-treat (ITT) population defined as all randomized subjects with non-missing data at baseline and at least one post-baseline visit. As a secondary analysis, the primary efficacy analysis will be performed using the ITT population. For all ITT-population analyses, missing efficacy data will be imputed from the last non-missing post-baseline visit carried forward to subsequent missing visits (LOCF).

For all analyses, two-tail alpha will be set to 0.05 with no adjustment for multiple comparisons. ANCOVAs will include Site in the model if doing so improves the sensitivity of the model for comparing treatment groups. As a sensitivity analysis, the primary efficacy analysis will also be run including Site and the Treatment-by-Site interaction. If the interaction term is associated with p < 0.10 then treatment group means for each Site will be examined individually to understand potential site differences. Sites with less than two completed blocks of subjects will be pooled with other such Sites to achieve new pooled analysis Sites that meet this criterion. Sites will

first be ranked by sample size and then pooled in that order until each new pooled analysis Site meets the two-block threshold.

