#### 6.1.3. Lesion Dimensions

At Visit 1, at Visit 2 prior to randomization, at Visit 4 prior to any retreatment study medication application and at Visit 8 the investigator will measure the length, the width and, at Visit 1 ONLY, the thickness (height) of the target lesion using the ruler provided, or an equivalent.

The investigator must measure the length and width of the target lesion as follows:

- Length (*i.e.*, the length of the longest axis) measured in millimeters (mm) and reported to the nearest mm
- Width (*i.e.*, the length of the longest axis perpendicular to the length) measured in millimeters (mm) and reported to the nearest mm.

At Visit 1 for the subject to be enrolled and at Visit 2 for the subject to be randomized the target lesion must have:

- A length (longest axis) that is ≥7mm and ≤15mm
- A width (longest dimension perpendicular to the longest axis) that is ≥7mm and ≤15mm.

At Visit 2, and Visit 4, the length and width must be measured prior to any study medication application.

At Visit 1 ONLY, the investigator must measure the thickness (height) of the target lesion above the surrounding skin, in mm reported to the nearest 0.5mm.

At Visit 1 for the subject to be enrolled, the target lesion must have a thickness that is  $\leq 2.0$ mm.

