#### 9.3. Sample Size

The sample size of 32 subjects per treatment group completing the study (as defined for the PP population) is based on previous data suggesting that the proportion of subjects with a clear lesion (PLA=0) at Visit 8 would be at least 0.325 for the highest active dose group with no more than 1 vehicle subject (a proportion of approximately 0.031) achieving a clear lesion at Visit 8. Under these assumptions this study would have approximately 87% power with two-tail alpha = 0.05, using the more conservative secondary efficacy endpoint. The ANCOVA analysis of the primary endpoint, mean change from baseline PLA for the PP population, is expected to be more sensitive than the above endpoint, with power greater than 90% under similar assumptions.

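### The primary ANCOVA names one covariate, baseline PLA, which can only be 2 or 3 and carries nothing on lateral lesion size; pre-specifying baseline lesion area could sharpen the comparison at almost no cost.

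*Combined protocol and SAP*

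**What the plan says.** Section 9.1 and the synopsis set the primary analysis as "mean change from baseline to Visit 8 PLA performed using Analysis of Covariance (ANCOVA) with baseline PLA as the covariate". Section 9.1 also has a conditional Site term: "ANCOVAs will include Site in the model if doing so improves the sensitivity of the model for comparing treatment groups". A sensitivity model adds Site and its interaction with treatment. No other baseline variable is named.

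Sections 5.3.2 and 6.1.2 require a PLA of 2 or more at randomization on an integer scale from 0 to 3. Grade 2 is a lesion up to 1 mm thick; grade 3 is thicker than 1 mm.

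Section 6.1.3 has length and width measured at Visit 1 and again at Visit 2 before randomization. The length criterion is "A length (longest axis) that is ≥7mm and ≤15mm", and width has the same limits. Thickness is recorded at Visit 1 only, when "the investigator must measure the thickness (height) of the target lesion above the surrounding skin, in mm reported to the nearest 0.5mm", with an upper limit of 2.0 mm.

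The synopsis lists lesion dimensions among the effectiveness evaluations, but Sections 9.1 to 9.3 do not mention them. Sections 5.7.3 and 5.7.4 describe 1:1:1 allocation and state no stratification by lesion size.

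**The concern.** Among randomized subjects, baseline PLA is a thin/thick indicator. Two lesions of the same grade can differ widely in area: the eligibility limits allow 7 × 7 = 49 mm² up to 15 × 15 = 225 mm², a ratio of 4.6. The covariate cannot see that difference.

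The protocol itself gives some reason to think size could matter. Section 5.7.6 sets the same application time and the same number of cycles whatever the lesion area, so contact time per unit area falls as area rises. PLA 0 requires that no lesion be visible at all.

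If area does predict Visit 8 PLA, the variation it explains now sits in the error term of every vehicle contrast, with a planned 32 completers per arm. At stake is the width of the confidence intervals, not the validity of the test.

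**Working it through.** **Inputs from the documents.** 32 completers per arm, 96 in all (Section 9.3, synopsis). Three arms. Two-sided alpha 0.05, unadjusted (Section 9.1). Stated power is about 87% for the proportion clear, and above 90% for the ANCOVA (Section 9.3).

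**Step 1: the plan's own figure.** Section 9.3 takes a clear rate of 0.325 in the 40% arm. For the vehicle arm it assumes "no more than 1 vehicle subject (a proportion of approximately 0.031) achieving a clear lesion at Visit 8". With p₁ = 0.325, p₂ = 0.031, n = 32 and pooled p = 0.178:

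- null SE = √(2 × 0.178 × 0.822 / 32) = 0.0956
- alternative SE = √((0.325 × 0.675 + 0.031 × 0.969) / 32) = 0.0883
- power = Φ((0.294 − 1.96 × 0.0956) / 0.0883) = Φ(1.207) = 88.6%

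Fisher's exact test gives 85.2%. The stated 87% therefore reproduces to within 2 points. It belongs to the secondary endpoint, which is tested by CMH, so ANCOVA covariates would not change it. The ANCOVA's figure cannot be reproduced, because no mean difference or SD of PLA change is given. Below, 90% is used as an illustrative anchor.

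**Step 2: cost and gain of adding area alone.** Without Site, the current model has 96 − 3 − 1 = 92 error degrees of freedom; adding area leaves 91. Let R² be the share of the remaining variance that area explains, given treatment and baseline PLA. Then

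SE ratio = √((1 − R²) × 92/91).

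Break-even is at R² = 1 − 91/92 = 0.011. Power from the 90% anchor is Φ((1.2816 + 1.96) / SE ratio − 1.96). Equivalent completers are 96 / (SE ratio)².

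| Assumed partial R² | SE ratio | Power from 90% | Equivalent completers |
|---|---|---|---|
| 0 | 1.005 | 90% (89.7%) | 95 |
| 0.05 | 0.980 | 91% | 100 |
| 0.10 | 0.954 | 92% | 105 |
| 0.20 | 0.899 | 95% | 119 |

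**Step 3: does thickness add anything?** PLA 2 versus 3 already divides thickness at 1 mm. Suppose thickness is 0.5, 1.0, 1.5 or 2.0 mm with equal frequency (an assumption). The mean is 1.25 and the variance 0.3125. The grade means are 0.75 and 1.75, so the between-grade variance is 0.25. The PLA split then explains 0.25 / 0.3125 = 80% of the thickness variance. Three other assumed distributions give 75% to 76%. Little independent thickness information may remain.

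**Step 4: all three dimensions.** Entering length, width and thickness separately costs three degrees of freedom. The break-even partial R² rises to about 0.033, and the confidence interval widens by 1.7% if they predict nothing. Area alone is the more economical choice.

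**The case against.** The strongest reply is that nothing here is wrong. The plan pre-specifies a valid ANCOVA adjusted for the baseline value of the outcome, and it contradicts no other section. That stands in full.

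Nor does any section link lesion size to Visit 8 PLA, and there are reasons to expect a weak link. PLA grades 1 to 3 turn on elevation and thickness, not area. The amount applied and the technique are adapted to lesion size. Lesions not clear at Visit 4 are generally retreated. Almost no vehicle lesions are expected to clear, so a common slope across arms may fit poorly. The 4.6-fold range compares the eligibility extremes and is not the spread among enrolled subjects. All of this stands, and it is why the gain is shown as a range that includes zero.

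A reader might infer more than the documents support:

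- *That precision is certainly being lost.* No prognostic strength is given. Below a partial R² of about 0.011, adding area slightly widens the interval.
- *That PLA is the only possible adjustment.* The conditional Site term is overlooked, although Site does not capture lesion size within a site.
- *That thickness is ignored.* Most of it is probably already coded by the PLA grade.
- *That chance imbalance in size biases the contrasts.* Randomization makes such imbalance part of the sampling error that the standard error and alpha already cover.
- *That power starts from 87%.* That figure is for the proportion clear; the ANCOVA is stated at above 90%.

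**Conclusion.** This is an inexpensive efficiency improvement, not an error. Baseline PLA is the only named covariate, can take only two values, and carries no information on lateral size. Length and width are scheduled for every subject before randomization and go unused in Section 9.

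The benefit is unknown from the documents. If area explains 5% to 10% of the remaining variance, standard errors fall by about 2% to 5%, worth roughly 4 to 9 extra completers. At 20% the fall is about 10%. From a 90% anchor, power gains about 1 to 5 points over partial R² of 0.05 to 0.20, and less if the ANCOVA's true power is already well above 90%. If area predicts nothing, standard errors rise by about 0.5%.

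These figures rest on the assumed R² values, the illustrative anchor, 96 completers and a model without Site. The trade is lopsided enough in favour of adjustment to recommend it, but leaving the plan unchanged would not undermine its conclusions.

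**What to change.** In Section 9.1 and the synopsis, before unblinding, name the primary covariates as baseline PLA and baseline lesion area, defined as Visit 2 length × width. State whether Visit 1 thickness is included; it is optional because it largely overlaps PLA. Apply the same set to the ITT rerun and the by-visit ANCOVAs.

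The cost is one sentence of analysis wording and one error degree of freedom. It needs no new data, visits or subjects. The choice should be fixed in advance, so that it cannot be seen as made in the light of the results.
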